3. STUDY DESIGN

This is an open-label, multi-center, single arm, Phase 1b study to evaluate the safety, efficacy and PK of avelumab in combination with axitinib as first line treatment in patients with advanced HCC.

Approximately 20 patients with advanced HCC who have not had prior systemic therapy will be enrolled in this study. The overall safety profile of these patients will be assessed after a minimum follow up of 3 months (ie. at least 3 months from last patient first dosing [LPFD]). Significant toxicities including irAEs which occur after 3 month follow up will also be included in the assessment.

Patients will receive avelumab 10 mg/kg Q2W in combination with axitinib 5 mg BID. If this dose level for the combination is not tolerable, a lower dose of the combination (avelumab 10 mg/kg IV Q2W plus axitinib 3 mg BID) may be evaluated with adding new cohort of patients. A cohort of patients aimed to evaluate avelumab 800 mg flat dose Q2W in combination with axitinib 5 mg BID may be added after the tolerability of avelumab 10 mg/kg Q2W in combination with axitinib 5 mg BID is confirmed.

Treatment with study drugs may continue until confirmed disease progression, patient refusal, patient lost to follow up, unacceptable toxicity, or the study is terminated by the sponsor, whichever comes first (see Section 6.3).

Patients who develop disease progression on study treatment but are otherwise continuing to derive clinical benefit from study treatment will be eligible to continue with avelumab combined with axitinib, single-agent avelumab, or single-agent axitinib provided that the treating physician has determined that the benefit/risk for doing so is favorable.

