2. STUDY OBJECTIVES AND ENDPOINTS

Primary Objective(s):	Primary Endpoint(s):

 To evaluate the safety and tolerability of avelumab in combination with axitinib as first line treatment in patients with advanced HCC. 	
 Adverse events (AEs) and laboratory abnormalities as graded by National Cancer Institute (NCI) Common Terminology Criteria for Adverse Events (CTCAE) v. 4.03.
Secondary Objective(s):	Secondary Endpoint(s):

 To evaluate antitumor effect of avelumab in combination with axitinib as first line treatment in patients with advanced HCC per RECIST v.1.1. To evaluate the OS of avelumab in combination with axitinib in patients with advanced HCC. To evaluate the pharmacokinetics of avelumab and axitinib when administered in combination. To evaluate candidate predictive biomarkers in pre-treatment tumor tissue that may aid in the identification of a patient subpopulation most likely to benefit from treatment with avelumab in combination with axitinib. To assess the immunogenicity of avelumab when combined with axitinib. 	
 Time to Progression (TTP), Progression Free Survival (PFS), Objective Response (OR), Disease Control (DC), Time to Tumor Response (TTR) and Duration of Response (DR), per RECIST v.1.1. Overall Survival (OS). PK parameters including trough and maximum concentrations (C_{trough}, C_{max}) of avelumab and axitinib. Tumor tissue biomarker status (ie, positive or negative based on, for example, PD-L1 expression and/or quantitation of tumor-infiltrating CD8+ T lymphocytes as assessed by immunohistochemistry [IHC]). Anti-drug antibodies (ADAs, neutralizing antibodies [nAbs]) for avelumab when in combination with axitinib.

CCI [REDACTED]
	
[REDACTED]

[REDACTED]
	
[REDACTED]

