Patients may withdraw from the study at any time at their own request, or they may be withdrawn at any time at the discretion of the investigator or sponsor for safety (see Section 8.1.3) or behavioral reasons, or the inability of the patient to comply with the protocol-required schedule of study visits or procedures at a given study site.

Reasons for withdrawal of study treatment may include:

- Objective disease progression. However, patients with disease progression who are continuing to derive clinical benefit from the study treatment will be eligible to continue with single-agent avelumab or axitinib, or with avelumab in combination with axitinib, provided that the treating physician has determined that the benefit/risk for doing so is favorable (see Section 5.4.3);
- Global deterioration of health status requiring discontinuation;
- Unacceptable toxicity. If the unacceptable toxicity is attributed to one of the two study treatments, the investigator (in discussion with the sponsor) may continue treatment with the other study treatment;
- Pregnancy;
- Significant protocol violation;
- Lost to follow-up;
- Patient refused further treatment (follow-up permitted by patient);
- Study terminated by sponsor;
- Death.

Reasons for withdrawal from study follow-up may include:

- Study terminated by sponsor;
- Lost to follow-up;
- Refused further follow-up;
- Death.

If a patient does not return for a scheduled visit, every effort should be made to contact the patient. All attempts to contact the patient and information received during contact attempts must be documented in the patient's medical record. In any circumstance, every effort should be made to document patient outcome, if possible. The investigator should inquire about the reason for withdrawal, request that the patient return all unused investigational product(s), request that the patient return for a final visit, if applicable, and follow up with the patient regarding any unresolved AEs.

If the patient withdraws from the study, and also withdraws consent for disclosure of future information, no further evaluations should be performed, and no additional data should be collected. The sponsor may retain and continue to use any data collected before such withdrawal of consent.

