9.1. Sample Size Determination

This study will enroll 20 patients to evaluate overall safety and tolerability with combination of avelumab plus axitinib. A sample size of 20 patients will provide at least 88% probability to observe at least one AE if the true incidence of the AE in the population is 10% or more.

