3.4. Baseline Variables

3.4.1. Study Drug, Study Treatment and Baseline Definitions

In this study, ‘study drug’ refers to avelumab or axitinib and ‘study treatment’ (or ‘treatment group’) refers to the following:

- avelumab 10 mg/kg in combination with axitinib 5 mg.

If avelumab 10 mg/kg in combination with axitinib 5 mg is not tolerable, a lower dose of the combination may be added as another treatment group evaluated in a new cohort of patients.

Start and end dates of study treatment:

The date/time of first dose of study treatment in a combination group is the earliest date/time of the first non-zero dose date/time for the study drugs in the combination.

The date/time of last dose of study treatment in a combination group is the latest date/time of the last non-zero dose date/time for the study drugs in the combination.

Definition of baseline:

The last available assessment prior to the start of study treatment is defined as ‘baseline’ value or ‘baseline’ assessment for safety, biomarker and efficacy analyses. If an assessment is planned to be performed prior to the first dose of study treatment in the protocol and the assessment is performed on the same day as the first dose of study treatment, it will be assumed that it was performed prior to study treatment administration, if assessment time point is not collected or is missing. If assessment time points are collected, the observed time

point will be used to determine pre-dose on study Day 1 for baseline calculation. Unscheduled assessments will be used in the determination of baseline. However, if time is missing, an unscheduled assessment on study Day 1 will be considered to have been obtained after study treatment administration.

Patients who start treatment and discontinue from the study on the same day may have two different sets of data collected on study Day 1 (one during study and one in the End of Treatment (EOT)) visit. Data reported at the EOT visit are not eligible for baseline selection.

If a scheduled pre-dose measurement actually occurred post-dose, then the corresponding measurement will be treated and analyzed similar to an unscheduled post-dose measurement.

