9. APPENDICES

Appendix 1. Immune-Related Adverse Events

The MedDRA PTs and clusters for irAEs are defined in the Safety Review Plan (SRP) for avelumab.

Immune-related AEs (irAEs) will be programmatically identified as outlined in Table 11. This case definition is hierarchical, ie, each step is only checked for patients and events that have already met the prior step.

Table 11. Case Definition for irAEs

Step	Selection Criteria	Additional Notes
1	Event selected based on a list of pre-specified MedDRA PTs within clusters. These are included in the SRP as Tier1 events (Immune-mediated xxxx). If AE matches the list then it is in for the next step	
2	AE onset during 1 st study drug administration or anytime thereafter through 90 days after last dose of study treatment	This is regardless of start of new anti-cancer drug therapy and regardless of TEAE classifications
3	Answer in the AE eCRF page to ‘Was another treatment given because of the occurrence of the event’ is ‘YES’	
4	AE treated with corticosteroids or other immunosuppressant therapy. For endocrinopathies only: AE required hormone replacement	Look in the conmed pages for AE identifiers that match the AEs from Step 3. For each of such AEs if A) OR B) OR C) below are met then the AE is in for the next step A) conmed ATC code is in (H02A, H02B, D07, A01AC, S01BA, S01BB, L04AA, L04AB, L04AC, L04AD, L04AX A07EA) and AE PT is in any of the irAE clusters. B) conmed ATC code is in (H03A, H03B) and AE PT is in one of the irAE clusters associated with “Immune-mediated endocrinopathies” C) conmed ATC code is A10A and AE PT is in the irAE cluster associated with “Immune-mediated endocrinopathies: Type I Diabetes Mellitus”

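### Adverse events that begin while a patient is on one drug alone are tabulated under the combination label, and no table shows how many there are

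*Protocol*

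**What the plan says.** **Objective.** Protocol Section 2 states the primary objective as "To evaluate the safety and tolerability of avelumab in combination with axitinib as first line treatment in patients with advanced HCC". The endpoint is graded adverse events and laboratory abnormalities.

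**Routes to single-agent treatment.** Protocol Section 3 says that patients who progress but still benefit "will be eligible to continue with avelumab combined with axitinib, single-agent avelumab, or single-agent axitinib". Under Protocol Section 6.3, when unacceptable toxicity is attributed to one drug, "the investigator (in discussion with the sponsor) may continue treatment with the other study treatment". The toxicity tables can also lead there: Table 3 ends avelumab after a Grade 3 or 4 infusion reaction, while Table 2 keeps axitinib going. No limit is set on time on one drug.

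**Window.** SAP Section 3.4.1 says the last dose of study treatment "is the latest date/time of the last non-zero dose date/time for the study drugs in the combination". SAP Sections 3.5.1 and 5.2.7 run the on-treatment period to 30 days after that date, or to the day before new anti-cancer drug therapy if earlier.

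**Tables.** SAP Sections 6.6.1, 6.6.3 and 6.6.5.1 use this one window for treatment-emergent events, serious events, Grade 3 or higher events and worst laboratory grade. SAP Section 4.2 labels patients by the first treatment received. SAP Section 6.6.1 calls an event related if it is related to at least one of the drugs.

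**Immune-related events.** SAP Appendix 1, Table 11, step 2 accepts onset from the first administration or "anytime thereafter through 90 days after last dose of study treatment", regardless of new anti-cancer drug therapy.

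**The concern.** The question is what happens to patients given the two drugs together. The tables also count what happens later on one of them, under the same label. In a single-arm study of 20 patients with no hypothesis test and no decision rule (SAP Sections 5.1.1 and 5.1.2), the descriptive tables carry the whole safety conclusion. Both documents make added cohorts depend on whether the starting dose of the combination is tolerable.

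A reader of those tables cannot tell whether a Grade 3 event arose in the second month on both drugs or long after one had stopped. The SAP already separates the drugs for exposure, disposition, and dose changes or discontinuations caused by adverse events. It does not do so for the onset of events, which is the primary endpoint.

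**Working it through.** **1. The plan's own figure.** Protocol Section 9.1 gives n = 20, a true incidence of 10%, and a probability of about 88% of seeing at least one event. Exact binomial: 1 − 0.9^20 = 0.878. The figure is reproduced to rounding, and the point does not change it. Applied to dual treatment alone, it would be 1 − 0.9^19 = 86.5% if one patient never received the second drug, and 1 − 0.9^18 = 85.0% if two did not.

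**2. How far the windows reach.** Suppose axitinib continues alone for G days after the last avelumab dose, with no new anti-cancer drug.
- The on-treatment window closes G + 30 days after the last avelumab dose.
- The immune-related window closes G + 90 days after it.

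For an assumed 4 to 8 months (122 to 244 days at 30.4375 days per month), these are about 152 to 274 days and 212 to 334 days. If avelumab is the drug that continues, the on-treatment window extends past the last axitinib dose in the same way.

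**3. Direction.** A patient counts once if any event occurs in the window, and the worst grade is a maximum over it. Lengthening the window can add patients or raise grades; it cannot remove them.

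**4. Size.** One patient of 20 is 1/20 = 5 points. The documents give no number of patients continuing on one drug, no duration and no event rate. The two illustrations below therefore rest on assumed inputs.

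*First Grade 3 or higher event.* Let k patients continue on one drug for m months with a monthly hazard h. Expected patients whose first such event falls in that time = k(1 − e^(−hm)).
- k = 4, h = 0.03, m = 4: 4(1 − e^(−0.12)) = 0.45 patients, or 2.3 points.
- k = 8, h = 0.08, m = 8: 8(1 − e^(−0.64)) = 3.78 patients, or 18.9 points.

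This treats all k patients as free of an earlier Grade 3 or higher event. In the renal cell study described in Protocol Section 1.2.4, 15 of 47 patients (31.9%) had a Grade 3 event. Removing that share multiplies both ends by 0.681: about 0.31 to 2.58 patients, or 1.5 to 12.9 points. The range falls further if most patients reach single-agent treatment through severe toxicity, because they are already counted.

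*Any one type of event.* Let p be its incidence on both drugs, f the share of patients with a single-agent phase, and q the new incidence in that phase. Reported incidence = p + (1 − p)fq. With p = 10%:
- f = 20%, q = 5%: 0.10 + 0.90 × 0.20 × 0.05 = 10.9%.
- f = 60%, q = 20%: 0.10 + 0.90 × 0.60 × 0.20 = 20.8%.

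That is 0.2 to 2.2 extra patients of 20. With p = 30% the range is 30.7% to 38.4%.

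**The case against.** The strongest reply is that the plan evaluates a first-line regimen whose rules let one component stop. Counting events until the regimen ends answers a proper regimen-level question and is a common convention. This stands. A reader might infer that the tables fail to answer the primary question; the documents do not support that. What is missing is a supportive breakdown.

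The SAP also offers partial help: per-drug exposure (Sections 6.5.3.1 and 6.5.3.2), a disposition cross-tabulation (6.5.2.1), per-drug tables of events leading to reduction, interruption or discontinuation (6.6.1.2 to 6.6.1.4), and full listings. Protocol Section 9.4.1.1 promises summaries by cycle, although SAP Section 6.6.1 lists none. None of these counts events by whether both drugs were being given.

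A reader might also infer that any late event treated with steroids becomes an immune-related event. Table 11 asks for more: a prespecified term, treatment for the event (step 3), immunosuppressant or hormone therapy (step 4), and an etiology or histology test (step 5), followed by possible medical review. These filter many late events. None of them specifies time since the last avelumab dose.

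A simple cut 30 days after the first drug stops would be open to objection itself. It would drop delayed avelumab events although adverse events are collected for at least 90 days (Protocol Section 8.1.4). It would mishandle avelumab re-treatment (Protocol Section 5.4.3), and it is undefined for a patient who receives only one drug. The fix below is built to meet these points.

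**Conclusion.** The point holds as a gap in reporting. Under SAP Sections 3.4.1, 4.2 and 5.2.7, events with onset during permitted single-agent treatment enter the combination tables, and no table shows their number. The effect on per-patient incidence and worst grade is upward only. The immune-related window, tied to the later drug, can stay open long after avelumab has stopped, subject to the further steps of Table 11.

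The certain part of the size is 5 points per affected patient. The illustrative range of about 0.3 to 2.6 patients of 20 for Grade 3 or higher events rests on assumed numbers, durations and hazards and on an earlier-event share borrowed from another tumour type. Its lower end is minor. A reader might infer that many patients will spend months on one drug. The documents permit this, and the primary cut-off is 18 months after the last patient is treated, but they give no expected number or duration. Protocol Section 5.4.3 treats continuation after confirmed progression as an exception to discontinuing.

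The change is worth making because it is cheap and affects what can be concluded about the combination. It does not invalidate the planned primary summary.

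**What to change.** Keep the whole-period tables as the main, regimen-level summary. In SAP Section 5.2.7 add a supportive combination-exposure period that ends at the earlier of:
- (a) 30 days after the last axitinib dose;
- (b) 90 days after the last avelumab dose, which matches the adverse event collection and immune-related windows;

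truncated at the existing end of the on-treatment period. State two rules with it: an avelumab gap before re-treatment that exceeds this window counts as single-agent time, and patients who never receive the second drug are shown separately.

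For this period, beside the existing tables, produce the overall adverse event summary, Grade 3 or higher treatment-emergent events, serious events and worst-grade laboratory tables. Flag single-agent onset in the adverse event listings. Report separately the immune-related events with onset more than 90 days after the last avelumab dose.

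The cost is SAP wording and one extra table set from per-drug dates already collected; no dose, visit, case report form or sample size changes. There are two limits. Rule (b) deliberately keeps events in the first 90 days after avelumab stops as combination events, so it reclassifies fewer events than the illustrations above count. The supportive tables also stop earlier for patients who stop one drug for toxicity, so they must be read beside the whole-period tables.

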4. SUBJECT ELIGIBILITY CRITERIA

This study can fulfill its objectives only if appropriate patients are enrolled. The following eligibility criteria are designed to select patients for whom participation in the study is considered appropriate. All relevant medical and nonmedical conditions should be taken into consideration when deciding whether a particular patient is suitable for this protocol.

Patient eligibility should be reviewed and documented by an appropriate member of the investigator's study team before patients are included in the study.

4.1. Inclusion Criteria

Patients must meet all of the following inclusion criteria to be eligible for enrollment into the study:

1. Diagnosis of locally advanced or metastatic HCC, obtained by histology/cytology (on a prior tumor biopsy) or by imaging (acceptable imaging modalities include triphasic contrast-enhanced helical computerized tomography [CT], triphasic dynamic contrast-enhanced magnetic resonance imaging [MRI] and contrast-enhanced ultrasonography) with serum α -fetoprotein (AFP) ≥ 400 ng/mL.
2. All patients must provide at least 1 archival tumor specimen. If archival tumor specimen is no longer available, *de novo* tumor biopsy will be required during screening.
3. HCC not amenable to local therapy.
4. Measurable disease according to RECIST v. 1.1.
5. Child-Pugh Class A disease (see [Appendix 2](#)). Score for hepatic encephalopathy must be 1; ascites score must be ≤ 2 .
6. Barcelona Clinic Liver Cancer (BCLC) stage B or C disease. Stage B disease must be unresectable, not amenable to local therapy or refractory to local therapy.
7. No evidence of uncontrolled hypertension as documented by 2 baseline blood pressure readings taken at least 1 hour apart. The baseline systolic blood pressure readings must be ≤ 140 mm Hg, and the baseline diastolic blood pressure readings must be ≤ 90 mm Hg. Patients whose hypertension is controlled by antihypertensive therapies are eligible.
8. Age ≥ 20 years.
9. ECOG performance status 0 or 1.
10. Estimated life expectancy of at least 3 months.
11. Required baseline laboratory data within the following parameters:
 - Neutrophils $\geq 1,500/\mu\text{L}$;
 - Platelets $\geq 75,000/\mu\text{L}$;
 - Hemoglobin ≥ 9.0 g/dL;
 - Serum aspartate aminotransferase (AST) and serum alanine aminotransferase (ALT) $\leq 5 \times \text{ULN}$;

- Estimated creatinine clearance ≥ 50 mL/min as calculated using the Cockcroft Gault (CG) equation;
 - INR < 1.7 or prothrombin time (PT) < 4 seconds above ULN (ie, Child-Pugh Score is no greater than 1);
 - Serum albumin ≥ 2.8 g/dL (ie, Child-Pugh Score is no greater than 2);
 - Total bilirubin ≤ 3 mg/dL (ie, Child-Pugh Score is no greater than 2);
 - Urinary protein $< 2+$ by urine dipstick. If dipstick is $\geq 2+$ then a 24 hour urine collection should be done and the patient may enter only if urinary protein is < 2.0 g per 24 hours.
12. Left ventricular ejection fraction (LVEF) \geq lower limit of normal (LLN) as assessed by multigated acquisition (MUGA) scan or echocardiogram (ECHO).
13. Serum or urine pregnancy test (for females of childbearing potential) negative at screening.
- Female patients of nonchildbearing potential must meet at least 1 of the following criteria:
- Achieved postmenopausal status, defined as follows: cessation of regular menses for at least 12 consecutive months with no alternative pathological or physiological cause; status may be confirmed with a serum follicle-stimulating hormone (FSH) level confirming the postmenopausal state;
 - Have undergone a documented hysterectomy and/or bilateral oophorectomy;
 - Have medically confirmed ovarian failure.
- All other female patients (including female patients with tubal ligations) are considered to be of childbearing potential.
14. Male patients able to father children and female patients of childbearing potential and at risk for pregnancy must agree to use 2 highly effective methods of contraception (see Section 4.3.1) throughout the study and for at least 30 days after the last dose of assigned treatment.
15. Evidence of a personally signed and dated informed consent document indicating that the patient has been informed of all pertinent aspects of the study.
16. Willing and able to comply with scheduled visits, treatment plan, laboratory tests, and other study procedures.

4.2. Exclusion Criteria

Patients with any of the following characteristics/conditions will not be included in the study:

1. Prior systemic treatment for advanced HCC, including prior treatment with approved or investigational drugs.
 - Prior immunotherapy with anti-PD-1, anti-PD-L1, anti-PD-L2, anti-CD137, or anti-cytotoxic T-lymphocyte-associated antigen-4 (CTLA-4) antibody (including ipilimumab), or any other antibody or drug specifically targeting T-cell co-stimulation or immune checkpoint pathways.
 - Prior therapy with sorafenib as well as any prior therapies with other VEGF pathway inhibitors.
2. Any prior locoregional therapy (such as hepatic arterial embolization, TACE, hepatic arterial infusion, radiofrequency ablation, percutaneous ethanol injection or cryoablation) within 4 weeks and radiotherapy or surgical procedure within 2 weeks (4 weeks for major surgery) of enrollment. Prior palliative radiotherapy to metastatic lesion(s) is permitted, provided it has been completed at least 48 hours prior to enrollment.
3. Persisting toxicity related to prior therapy (NCI CTCAE v. 4.03 Grade >1); however alopecia, sensory neuropathy Grade ≤ 2 , or other Grade ≤ 2 AEs not constituting a safety risk based on investigator's judgment are acceptable.
4. Patients with known symptomatic brain metastases requiring steroids. Patients with previously diagnosed brain metastases are eligible if they have completed their treatment and have recovered from the acute effects of radiation therapy or surgery prior to starting the study treatment, have discontinued corticosteroid treatment for these metastases for at least 4 weeks and are neurologically stable.
5. Presence of hepatic encephalopathy (ie, Child-Pugh score of 2 or 3) and/or clinically relevant ascites (ie, Child-Pugh score of 3).
6. Presence of **main** portal vein invasion by HCC (invasion to 1st or 2nd branch of portal vein is acceptable).
7. NCI CTCAE Grade ≥ 3 hemorrhage within 4 weeks of enrollment, or variceal hemorrhage of any grade within 12 months of enrollment.
8. Evidence of inadequate wound healing.
9. History of abdominal fistula, gastrointestinal perforation, or intra-abdominal abscess within 28 days of enrollment.
10. Any of the following within the 12 months prior to enrollment: myocardial infarction, severe/unstable angina, coronary/peripheral artery bypass graft, symptomatic

- congestive heart failure, LVEF less than LLN, clinically significant pericardial effusion, cerebrovascular accident, transient ischemic attack.
11. Any of the following in the previous 6 months: deep vein thrombosis or symptomatic pulmonary embolism.
 12. Ongoing cardiac dysrhythmias of NCI CTCAE Grade ≥ 2 or prolongation of the QTc interval to >500 msec.
 13. Evidence of tumor involvement of the myocardium or pericardium or tumor thrombus extending to the heart.
 14. History of or known active seizure disorder, spinal cord compression, or carcinomatous meningitis, or new evidence of brain or leptomeningeal disease.
 15. Known prior severe hypersensitivity to investigational product or any component in its formulations, including known severe hypersensitivity reactions to monoclonal antibodies (NCI CTCAE v. 4.03 Grade ≥ 3).
 16. Current use of immunosuppressive medication at the time of enrollment, except the following: a. Intranasal, inhaled, topical steroids, or local steroid injections (eg, intra-articular injection); b. Systemic corticosteroids at physiologic doses ≤ 10 mg/day of prednisone or equivalent; c. Steroids as premedication for hypersensitivity reactions (eg, CT scan premedication).
 17. Active autoimmune disease that might deteriorate when receiving an immunostimulatory agents. Patients with type I diabetes mellitus, vitiligo, psoriasis, hypo- or hyperthyroid disease not requiring immunosuppressive treatment are eligible.
 18. Active infection requiring systemic therapy except for hepatitis C virus (HCV) and hepatitis B virus (HBV) as follows:
 - Patients with chronic infection by HCV are eligible for study participation.
 - Patients with chronic infection by HBV are eligible for study participation only if they are on antiviral therapy and the infection is controlled by treatment prior to enrollment.
 19. Administration of a live vaccine within 28 days prior to enrollment.
 20. Current use or anticipated need for treatment with botanical formulation having an approved indication for liver cancer treatment, such as “Kanglaite”
 21. Current use or anticipated need for treatment with drugs or foods that are known strong CYP3A4/5 inhibitors, including their administration within 10 days prior to patient starting the study treatment (eg, grapefruit juice or

- grapefruit/grapefruit-related citrus fruits [eg, Seville oranges, pomelos], ketoconazole, miconazole, itraconazole, voriconazole, posaconazole, clarithromycin, telithromycin, indinavir, saquinavir, ritonavir, nelfinavir, amprenavir, fosamprenavir nefazodone, lopinavir, troleandomycin, mibefradil, and conivaptan). The topical use of these medications (if applicable), such as 2% ketoconazole cream, is allowed.
22. Current use or anticipated need for drugs that are known strong CYP3A4/5 inducers, including their administration within 10 days prior to patient starting the study treatment (eg, phenobarbital, rifampin, phenytoin, carbamazepine, rifabutin, rifapentin, clevidipine, and St John's wort).
 23. Requirement of anticoagulant therapy with oral vitamin K antagonists. Low-dose anticoagulants for maintenance of patency of central venous access device or prevention of deep venous thrombosis is allowed. Therapeutic use of low molecular weight heparin is allowed.
 24. Gastrointestinal abnormalities including:
 - Inability to take oral medication;
 - Requirement for intravenous alimentation;
 - Prior surgical procedures affecting absorption including total gastric resection;
 - Treatment for active peptic ulcer disease in the past 6 months unless the ulcer is completely healed as confirmed by endoscopy prior to study treatment;
 - Active gastrointestinal bleeding, unrelated to cancer, as evidenced by hematemesis, hematochezia or melena in the past 3 months without evidence of resolution documented by endoscopy or colonoscopy;
 - Malabsorption syndromes.
 25. Prior organ transplantation including allogenic stem-cell transplantation
 26. Known history of testing positive for human immunodeficiency virus (HIV) or known acquired immunodeficiency syndrome.
 27. Diagnosis of any other malignancy within 3 years prior to enrollment, except for adequately treated basal cell or squamous cell skin cancer, or carcinoma in situ of the breast or of the cervix, low-grade (Gleason 6 or below) prostate cancer on surveillance with no plans for treatment intervention (eg, surgery, radiation, or castration), or pathologically diagnosed in situ gastric (T1 [M]; UL [-]), esophageal (T1S or T1a), or colorectal cancer (Stage 0 [M]) treated with curative resection.
 28. Investigator site staff members directly involved in the conduct of the study and their family members, site staff members otherwise supervised by the investigator, or

- patients who are Pfizer employees, including their family members, directly involved in the conduct of the study.
29. Participation in other studies involving investigational drug(s) within 4 weeks prior to enrollment.
 30. Concurrent colitis, inflammatory bowel disease, pneumonitis, pulmonary fibrosis
 31. Other acute or chronic medical or psychiatric condition including recent (within the past year) or active suicidal ideation or behavior or laboratory abnormality that may increase the risk associated with study participation or investigational product administration or may interfere with the interpretation of study results and, in the judgment of the investigator, would make the patient inappropriate for entry into this study.
 32. Pregnant female patients; breastfeeding female patients.

